## 27.0 Data Analysis\*

8.

1. *Describe the data analysis plan, including any statistical procedures or power analysis.*

*Describe how the sample size for the study was determined (e.g. formal sample size calculation, convenience sampling). To minimize the risks associated with a possible breach of confidentiality, appropriate sample size calculations limit the amount of patient data being recorded to the amount necessary to answer the research question.*

Quantitative data: We will conduct descriptive analysis with inferential and graphical exploratory analytic techniques, presenting mean, median, and interquartile range [continuous variables] and frequency and percentage [categorical variables]. We will examine outliers and/or influential points, perform bivariate analyses to assess relationships, and summarize group data. We will use SAS 9.4 (SAS Institute Inc., Cary, NC, USA); the significance level will be 0.05. For our primary outcome, we calculate the proportion in each arm with any health care utilization at 6 months. We use logistic regression to assess intervention effect on utilization and explore differences in other outcomes. Models will include covariates to adjust for variables (e.g., sex, age) that may increase precision. We will explore heterogeneity of effects with stepwise addition on interaction terms to examine moderation by sex, age, or engagement. If >20% of data is missing, we will use complete cases or imputation, based on missingness pattern.

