Increasing Teen Access to Care (AccessKCTeen2)

NCT05444855

05 September 2023

Statistical analysis plan

We will use R software (R Foundation for Statistical Computing) for analyses. We will conduct descriptive analysis with inferential and graphical exploratory analytic techniques, presenting mean, median, and interquartile range [continuous variables] and frequency and percentage [categorical variables]. Next, bivariate analyses will be conducted to assess the relationship between variables. We will examine data for outliers and/or high leverage points and use established best practices in decided how to address them.

We will compare outcomes using independent t-tests for continuous variables and Chi-Square or Fisher's exact test for categorical variables depending on cell counts. If continuous variables are highly skewed nonparametric testing will be implemented (i.e., Wilcoxon rank-sum test). All tests will be two-sided, assessed with significance of $p<0.05$. We will evaluate these feasibility constructs:(acceptability, demand, implementation, practicality, integration, expansion, limited efficacy [see primary outcome]) using descriptive statistics. *Primary outcome:* We will calculate the proportion of adolescents with any health care utilization at 6 months.

Attrition: We will use established methods to minimize attrition (see "Recruitment and Retention") and plan to assess for our primary outcome every two months to keep participants engaged and minimize bias. Participants who are lost to follow-up after three attempts at 6 months will be excluded from the denominators for hypothesis testing. We will report on demographics of those lost to follow-up compared to those who completed the study.

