Missing data: We plan to minimize missing data by engaging our CAB to pretest survey measures to achieve brevity and clarity. Our electronic data collection tool (REDCap) can be set to require participant responses before advancing. In order to identify potential problems promptly, we will run a REDCap report every second week to review the degree of missingness for each variable. Any variable missing $>5\%$ will be reviewed to determine probable causes and a plan will be developed to address the issue(s). During analysis, we will determine both the extent of missingness and whether data are missing at random (MAR). If the data are missing for $<20\%$ of responses, we will rely on list-wise deletion. If $\geq 20\%$ is missing we will utilize multiple imputation techniques. Specifically, we will determine if data are MAR by partitioning the data into two groups (those with and without missing data) and examining the distributions across variables of interest and employ appropriate imputation techniques.

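### The SAP sets no denominator for the primary proportion: participants lost at month 6 are likely to drop out of it, their month-2 and month-4 answers have no assigned use, and nothing bounds the effect of loss

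*SAP*

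**What the plan says.** The SAP states the primary analysis in one sentence: "We will calculate the proportion of adolescents with any health care utilization at 6 months". It names no denominator there. The next paragraph, Attrition, holds the only denominator rule in either document: "Participants who are lost to follow-up after three attempts at 6 months will be excluded from the denominators for hypothesis testing". In the same paragraph the authors "plan to assess for our primary outcome every two months to keep participants engaged and minimize bias", so the outcome is also collected at months 2 and 4. For those lost, that paragraph plans one analysis: "We will report on demographics of those lost to follow-up compared to those who completed the study".

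The SAP's Missing data paragraph sets a threshold. Where data are missing for under 20% "of responses, we will rely on list-wise deletion"; where 20% or more "is missing we will utilize multiple imputation techniques". Whether data are missing at random is to be judged by splitting the data by missingness and "examining the distributions across variables of interest".

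The protocol is looser. Section 27.0 says that above 20% missing "we will use complete cases or imputation, based on missingness pattern". It gives no denominator either. Section 24.1 keeps the baseline data of non-completers for analysis and does not mention their month-2 or month-4 answers. The feasibility table in section 9.0 lists study and medical records, beside the adolescent, as a source for the construct that contains health care utilization. Section 25.0 says that all data come directly from participants.

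**The concern.** The primary result is a single proportion, so its denominator is part of its definition. Two analysts working from this text could report different primary figures from the same data: one on completers, one on everyone enrolled with imputation.

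If teens who stop answering use care at a different rate from those who stay, the completers-only figure is off, and the direction is unknown. The answers most likely to reduce that error are those already given at months 2 and 4. The SAP says the repeated assessment is meant to limit bias, but no analysis step uses it for a teen missed at month 6.

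The documents also do not say whether the outcome is cumulative from enrolment. If it is, a teen who reported care use at month 2 has a known outcome and may still be dropped. If it covers a recent window, the earlier answers are good predictors left unused.

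The two planned comparisons describe who is missing. Neither shows how far the primary proportion could move.

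**Working it through.** There is no figure of the plan's own to reproduce: neither document gives an expected utilization rate, an expected retention rate or a sample-size calculation. Protocol 7.0 gives a ceiling of 250 adolescents. The loss fractions, care-use rates and smaller cohort sizes below are assumptions.

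**Step 1: which denominator follows from the text?**

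| Reading of the SAP's Missing data paragraph | Result for those lost at month 6 |
|---|---|
| Covers them, under 20% missing | Deleted: completers only |
| Covers them, 20% or more missing | Imputed: conflicts with the Attrition exclusion for any test, and no text says which prevails |
| Covers skipped items only | Excluded from tests; nothing is written for the primary proportion |

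Two of the three branches lead to completers only or to silence, and the third is unreconciled.

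**Step 2: size of the shift.** Let L be the fraction lost, p the rate in completers and q the rate in those lost. The rate in all enrolled is (1 − L)p + Lq, so the error of the completers-only figure is p − [(1 − L)p + Lq] = L(p − q). It is zero when p = q and does not depend on N. With p − q = 20 points:
- L = 10%: 0.1 × 20 = 2 points
- L = 20%: 0.2 × 20 = 4 points
- L = 30%: 0.3 × 20 = 6 points

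**Step 3: outer bounds.** Setting all lost to no gives (1 − L)p; setting all to yes gives (1 − L)p + L. At p = 50%:
- L = 10%: 45% to 55%
- L = 20%: 40% to 60%
- L = 30%: 35% to 65%

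**Step 4: comparison with sampling error** (L = 20%, p = 50%, Wilson 95% interval among completers). The break-even gap is the half-width divided by 0.2.

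| Enrolled | Yes / completers | 95% interval | Half-width (points) | Break-even gap (points) |
|---|---|---|---|---|
| 250 | 100/200 | 43.1% to 56.9% | 6.86 | 34.3 |
| 150 | 60/120 | 41.2% to 58.8% | 8.81 | 44.0 |
| 100 | 40/80 | 39.3% to 60.7% | 10.70 | 53.5, not attainable |

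With completers at 50%, the gap cannot exceed 50 points. At 100 enrolled, the 40% to 60% bounds therefore lie inside the interval, and bias cannot exceed sampling error. These intervals treat teens as independent. Recruitment runs through friend networks (protocol 8.0), and positive clustering would widen the intervals and raise the break-even gaps.

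**Step 5: what the earlier answers could add if the outcome is cumulative** (250 enrolled, 50 lost, 100 of 200 completers yes). Suppose 5 to 25 of the 50 lost had already said yes.
- Keeping those yes answers and setting the rest to no gives (100 + 5)/250 = 42% to (100 + 25)/250 = 50%, against 100/250 = 40% when the answers are ignored. Each earlier yes raises the lower bound by 1/250 = 0.4 points.
- Adding only the known yes cases to numerator and denominator gives 105/205 = 51.2% to 125/225 = 55.6%. This pushes the figure up by construction, because no lost teen without a yes is counted.

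**The case against.** The strongest reply is that the exclusion is worded for hypothesis tests, while the primary outcome is a descriptive proportion. That stands. A reader might infer that the SAP prescribes a completers-only primary proportion; it does not. What remains is that no other denominator is written.

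A second reply is size. A reader might infer that loss would swamp sampling error. Step 4 does not support that: at 50% use and 20% loss, those lost would need a rate of about 16% or less, or 84% or more, with 250 enrolled. With 100 enrolled it cannot happen. The hypothesis is about feasibility and no success threshold is set. Gift cards for each follow-up survey, up to three attempts per survey and several contact channels should limit loss. All of this lowers the stakes.

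Third, imputation is planned. It is, but only at 20% or more, and the SAP does not say that it reaches people whom the Attrition paragraph removes.

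Fourth, records could supply outcomes for non-responders, given the source column in protocol 9.0. Section 25.0 cuts both ways: it marks the medical record number as recorded, but says all data come from participants and that the clinical care data are de-identified. Neither document says whether records are used for those lost.

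Fifth, the survey appendix may define the recall window, and the SAP cites a recruitment and retention section that is in neither document. Neither could be checked. A defined window would still not settle the denominator.

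Two further inferences fail. Baseline data of non-completers are not left without a use: the two planned comparisons can use them. Event-day participants are unlikely to enter a 6-month denominator, because they complete a single survey and protocol 11.0 gives them no follow-up; naming the population is enough.

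**Conclusion.** The point holds as a gap in the analysis rule, with modest consequences. The denominator of the primary proportion is unstated and completers-only is its likely form. Earlier answers on the same outcome have no assigned use when month 6 is missing. The exclusion and the 20% rule are not reconciled, and no planned analysis bounds the effect of loss.

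Under the assumed inputs, a 20-point difference in care use moves the estimate by 2 to 6 points at 10% to 30% loss. At 20% loss and 50% use, the outer bounds exceed the 95% interval by about 3 points on each side with 250 enrolled (40 against 43.1; 60 against 56.9) and by about 1 point with 150. With 100 enrolled they do not exceed it. The direction cannot be derived from the documents. This is a cheap improvement of minor to moderate weight. The protocol's differing statements on when contact details are destroyed are a separate matter and carry no weight here.

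**What to change.** In the SAP:
- Name all enrolled intervention trial participants as the denominator of the primary proportion.
- State whether the outcome is cumulative from enrolment to 6 months or covers a recent window.
- For participants with no month-6 outcome, use multiple imputation with month-2 and month-4 answers and baseline data. If the outcome is cumulative, hold a reported yes fixed, and do not simply add known yes cases back to the completers.
- Add an all-no/all-yes bound, since the imputation rests on data being missing at random. Report the completers-only proportion alongside.
- State how the 20% rule applies to those lost to follow-up, and how it fits with the Attrition exclusion.
- Say whether utilization from study or medical records is used for those lost.

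In the protocol, align sections 24.1 and 27.0 with this rule.

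The cost is wording in both documents and modest analysis time, with no new data collection. The downside is a slightly longer analysis and possibly a wider interval around the primary proportion.
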